## 9. INVESTIGATIONAL MEDICINAL PRODUCT (IMP)

### 9.1 Investigational Medicinal Product Description

#### 9.1.1 MV-ZIKA-RSP vaccine-test product

The MV-ZIKA-RSP vaccine candidate is a live attenuated recombinant viral vectored vaccine for prophylaxis of Zika virus infection. [redacted]

[redacted] chemically synthesized and inserted into the Schwarz vaccine strain of measles virus (MV) to produce the candidate vaccine MV-ZIKA-RSP (further details under section 4.1; also refer to IB and IMPD).

The MV-ZIKA-RSP vaccine is provided by the sponsor in glass vials.

The study drug used in the study is a liquid frozen suspension for injection with an extractable dose of:

High dose: Concentration:  $3.0 \times 10^5$  TCID50 per vial

Low dose: Concentration:  $6.0 \times 10^4$  TCID50 per vial

Two dosages will be administered to the participants:

High dose: Concentration: 0.5 mL  $1 \times 10^5$  TCID50/dose

Low dose: Concentration: 0.5 mL  $2.5 \times 10^4$  TCID50/dose

Dosage strengths have been selected based on experience with this type of vaccine (Schwarz strain measles virus vectored vaccine).

Liquid frozen MV-ZIKA-RSP vaccine will be thawed at room temperature (for about 30 min), 0.5 mL will be drawn up into a 1-mL syringe. The preparer may inject the subject or can hand over the syringe to an injector. The injecting preparer must not participate in the study as observer; the injector, if participating in later study conduct must be blinded (e.g. by blinding the content of the syringe with the provided syringe label).

#### 9.1.2 Placebo

A sterile physiological saline solution will be used as placebo to ensure blinding of the treatment schedule in case of single vaccination regimen (treatment group C and D). The physiological saline solution (0.9% NaCl) is a clear colourless solution ready to use, stored at room temperature and provided by the study site.

## 9.2 Packaging and Labelling

Individual cardboard boxes will contain single 2 ml transparent glass vials, with rubber stopper and aluminium seal, containing frozen liquid. The labels on vials and boxes will be in English language.

For further details of IMP labelling, please refer to the study specific IMP-Manual.

## 9.3 Dose Regimen

All 48 eligible participants will receive at their first treatment MV-ZIKA-RSP, at Visit 1 (day 0), and 4 weeks later the second treatment either with MV-ZIKA-RSP or placebo, at Visit 2 (day 28 ±3)

| Visit           | VS | Visit 1 | Visit 2 | Visit 3 | Visit 4 |
|-----------------|----|---------|---------|---------|---------|
| Study Day       |    | 0       | 28 ±3   | 56 ±3   | 182 ±14 |
| Study Treatment |    | ①       | ②       |         |         |

The 4 treatments groups (A, B, C and D) differ in the concentration of MV-ZIKA-RSP, as well as, in single or double shot treatment regimen.

Group A: MV-ZIKA-RSP 1 x10^5 (±0.5 log) TCID50 /dose day 0 and day 28

Group B: MV-ZIKA-RSP 2,5 x10^4 (±0.5 log) TCID50 /dose day 0 and day 28

Group C: MV-ZIKA-RSP 1 x10^5 (±0.5 log) TCID50 /dose day 0 and placebo day 28

Group D: Placebo day 0 and day 28

## 9.4 Justification of Clinical Dose Regime

Two different doses of MV-ZIKA: 2,5x10^4 (± 0.5 log) - low dose- and 1x10^5 (± 0.5 log) -high dose- 50% tissue culture infective dose (TCID50) will be assessed in healthy adults for safety and immunogenicity as determined by the induction of functional, neutralizing antibodies (Table 4). A dose of 2x10^6 TCID50 was assessed for toxicity in a GLP compliant repeated dose toxicity study. The 20-fold higher dose compared to the clinical dose showed no adverse local or systemic effects.

The clinical dose was selected based on findings in non-clinical pharmacology studies, clinical dose finding studies of comparable vaccine candidates and on assessment for cost-effective manufacturing of a vaccine for use in low-and middle-income countries. A dose of 1x10^5 TCID50

in NHP conferred 100% protection against Zika virus challenge. In addition, clinical trial on a comparable, measles vector-based vaccine candidate against Chikungunya virus (CHIKV) was effective and safe in the here proposed dose range. A dose of  $5 \times 10^5$  TCID50 induced up to 100% seroconversion in healthy adult subjects after two immunizations.

[REDACTED] However, a reduction to a potentially highly effective lower dose will substantially affect manufacturing costs. Zika virus is predominantly endemic in low- and middle-income countries. Thus, a vaccine will need to meet the qualitative and economical requirements.

Table 4. Dose regime

| Treatment Group | N  | Vaccine                               | Formulation                  | Vaccine on day   | Placebo on day    |
|-----------------|----|---------------------------------------|------------------------------|------------------|-------------------|
| A               | 14 | MV-ZIKA-RSP 1 $\times 10^5$ /0.5 ml   | liquid frozen                | 0 + 28           |                   |
| B               | 14 | MV-ZIKA-RSP 2,5 $\times 10^4$ /0.5 ml | liquid frozen                | 0 + 28           |                   |
| C               | 12 | MV-ZIKA-RSP 1 $\times 10^5$ /0.5 ml   | liquid frozen/placebo liquid | 0                | Placebo on day 28 |
| D               | 8  | Placebo/0.5 ml                        | liquid                       | Placebo on day 0 | Placebo on day 28 |

## 9.5 Storage and Transport Conditions

The IMP must be stored under continuously temperature-controlled condition in a lockable room, or lockable freezer with limited access.

The minimum and maximum temperature will be recorded daily in the temperature logs throughout the study, except on weekends and holidays if min/max thermometer will be used.

In case the freezer/fridge is connected to an alarm system and corresponding copies of the readout can be filed, a min/max temperature does not need to be recorded daily. It is acceptable to use a site-specific temperature log, which covers all the required information.

MV-ZIKA-RSP have to be kept in the outer package to be protected from light.

The liquid frozen formulation of MV-ZIKA-RSP will be stored and transported at -80°C and shall be administered within 30 min after preparation, the ready to use formulation can be stored at 2-8°C for up to 1 hour.

The 0.9% saline solution and sterile water diluent will be stored according to instruction leaflet. It is under the site's responsibility to ensure the storage conditions according to the summary product characteristics.

After administration, all used containers properly labelled with subject ID and appropriate visit identifier (e.g. visit number, date of administration) will be stored at site until checked for accountability by the unblinded monitor.

## 9.6 IMP Preparation and Distribution

MV-ZIKA-RSP and placebo will be prepared and administered by unblinded, authorised and qualified staff members (investigator, pharmacist, or nurse) otherwise not involved in the conduct of the trial after randomisation. Preparation of MV-ZIKA-RSP for injection will be performed in a dedicated lab appropriate for handling of GMOs applying biosafety level 2 (BSL2) standards although MV-ZIKA-RSP are assessed as a biosafety level 1 product. BSL2 is applied because there is a negative system biological safety level 2 cabinet available within a containment room, which usually is used for preparing IMPs.

MV-ZIKA-RSP and placebo will be exclusively used for the present clinical trial and will only be administered to participants enrolled in the study.

For detailed description of receipt, storage, preparation, accountability, and destruction of IMP, please refer to the study specific IMP-Manual.

## 9.7 GMO Handling

MV-ZIKA-RSP vaccine are a genetically modified organism requiring biosafety level 1 standards. Nevertheless, preparation and disposal of IMP will be performed in a dedicated lab according to applicable hygiene standards of biosafety level 2. Needles and syringes that have been in contact with MV-ZIKA-RSP, as well as all other potentially contaminated materials, will be collected in dedicated containers and will be destroyed in a safe manner.

This study will be conducted under regulations for contained use of a GMO.

## 9.8 Route and Method of Administration of IMP

All participants will receive intramuscular (i.m.) injections of MV-ZIKA-RSP vaccine or placebo in the deltoid region of the non-dominant arm (preferred) or the dominant arm. In case of ongoing local AEs from previous vaccinations at the respective injection site, vaccination in the contra-lateral arm should be performed.

## 9.9 Treatment Compliance

The study medication will be prepared at site and administered during the study Visit 1 and 2. Each treatment will be documented in the subject's charts, the eCRF, an IMP Preparation Log and an IMP Inventory Log. Participants must receive all assigned vaccinations to be considered compliant.

## 9.10 Study Drug Accountability

IMP accountability will be performed throughout the entire study, starting with the initial receipt of medication.

The authorised, unblinded study staff members will confirm the number and condition of received vials, by signing and dating an IMP receipt form.

Upon receipt an IMP inventory log will be kept current by the site, detailing the batch numbers, dates and quantity of IMP obtained, used for administration on a per subject basis and destroyed or returned to the sponsor. This documentation will only be available to an unblinded monitor verifying drug accountability during the study.

At the end of the study, all unused and used MV-ZIKA-RSP vials (marked with subject ID and visit number) will be returned to the sponsor or destroyed by the investigator in a confidential manner, after final reconciliation and confirmation of correctness of drug accountability.

## 9.11 Prior and Concomitant Therapy

### 9.11.1 Permitted Prior and Concomitant Therapy

Any prior vaccination within the last three years prior screening and any medication within 30 days prior screening has to be documented.

Any medication taken during the study up to Visit 4 (study day 182) has to be reported to the investigator and will be documented.

Additionally, any treatment that will be considered necessary for the subject's welfare may be given at the discretion of the Investigator. All concomitant medications must be reported in the appropriate section of the eCRF along with dosage information, dates of administration, and reasons for use. Generic names for concomitant medication should be preferred, if possible.

All concomitant medications will be coded using the WHO Drug Dictionary.

### 9.11.2 Forbidden Prior and Concomitant Therapy

Treatments with non-study licensed vaccines within 4 weeks prior to first study vaccination until the end of the study (day 182) are not allowed.

Use of immunosuppressive drugs like corticosteroids (excluding topical preparations) within 30 days prior to the first vaccination or anticipated use before completion of the study (day 182) is not allowed.

Receipt of blood products or immunoglobulins within 120 days prior to the Screening Visit or anticipated receipt of any blood product or immunoglobulin before completion of the study (day 182) is not allowed.

Participants must be asked about concomitant medication and vaccinations at each visit. Any concomitant medication or vaccination must be documented.

## 10. SAFETY REPORTING

### 10.1 Definitions

#### 10.1.1 Adverse Event (AE)

Any untoward medical occurrence in a participant to whom an investigational medicinal product (IMP) has been administered, not necessarily caused by or related to that product.

An AE can therefore be any unfavourable or unintended sign, abnormal laboratory finding, symptom or disease temporally associated with the use of an IMP whether or not considered related to the IMP.

#### 10.1.2 Clinical Laboratory Adverse Event

A clinical laboratory AE is any clinical laboratory abnormality that suggests a disease and/or organ toxicity and is of a severity, which requires active management (i.e., changes of dose, discontinuation of drug, more frequent follow-up or diagnostic investigation).

#### 10.1.3 Adverse Reaction (AR)

An untoward and unintended response in a participant to an investigational medicinal product which is at least possibly related to any dose administered to that participant.

All cases judged by either the reporting medically qualified professional or the sponsor as having a reasonable suspected causal relationship to the trial medication qualify as adverse reactions.

#### 10.1.4 Serious Adverse Event (SAE)

A serious adverse event is any untoward medical occurrence that:

- results in death
- is life-threatening
- requires inpatient hospitalisation or prolongation of existing hospitalisation
- results in persistent or significant disability/incapacity
- consists of a congenital anomaly or birth defect

Other 'important medical events' may also be considered serious if they jeopardise the participant or require an intervention to prevent one of the above consequences.

The term "life-threatening" in the definition of "serious" refers to an event in which the participant was at risk of death at the time of the event. It does not refer to an event which hypothetically might have caused death if it were more severe.

Any pregnancy occurring during the clinical trial and the outcome of the pregnancy will be recorded and followed up for congenital abnormality or birth defect, at which point it would fall within the definition of "serious".

NOTE: to avoid confusion or misunderstanding of the difference between the terms "serious" and "severe", the following note of clarification is provided: "Severe" is used to describe the intensity of a specific adverse event, while "seriousness" is used for defining regulatory reporting obligations as supplied above.

### **10.1.5 Suspected Unexpected Serious Adverse Reaction (SUSAR)**

A serious adverse reaction, the nature, severity, or outcome of which is not consistent with the applicable product information.

### **10.1.6 Causality**

The relationship of each AE to the IMP must be determined by a medically qualified person according to the following definitions:

Definitely: Temporal relationship to the administration of the study drug and course following a known reaction pattern

Probably: Good reasons and sufficient documentation to assume a causal relationship

Possibly: A causal relationship is conceivable and cannot be dismissed

Unlikely: The event is most likely related to an etiology other than the trial treatment

Not Related: No temporal relationship to the administration of the drug or other factors have caused the event

### **10.1.7 Severity**

AEs must be graded by a medically qualified person as being mild, moderate, severe, or life-threatening and their approximate duration given. Definitions of severity are as follows:

Mild: an AE that requires minimal or no treatment and does not interfere with daily activities.

Moderate: an AE that is sufficiently discomforting to interfere with normal activities.

Severe: an AE that is incapacitating or prevents normal activities and may require systemic drug therapy or other treatment.

Potentially life threatening: an AE that requires immediate intervention to prevent death.

"life-threatening" refers to an AE in which the subject was at risk of death at the time of the event, it does not refer to an AE which hypothetically might have caused death if it were more severe.

Please see Appendix 1 for stencil to be used for grading local injection site reactions and Table 5 and 6 for grading of systemic and local reactions.

### **10.1.8      Expectedness**

Expectedness will be determined considering the current Investigators' Brochure.

Expected: an AE that is listed in the current Investigator's Brochure of MV-CHIK.

Unexpected: an AE that is not listed in the current Investigator's Brochure or differs due to greater severity or greater specificity.

All SAEs assessed as unexpected and suspected to be related to the IMP qualify for a SUSAR (suspected unexpected serious adverse reaction) and require expedited reporting.

### **10.1.9      Outcome**

Recovered: A subject has recovered from an AE, when all signs or symptoms returned to normal.

Stabilised: An AE is stabilised when, according to the investigator, the subject is in a clinically stable condition. This term should only be used for chronic conditions and for a given subject only when he/she has completed the study.

Recovered with sequelae: As a result of the SAE, the subject is suffering from persistent or significant disability/incapacity (e.g. became blind, deaf, paralysed). Any AE recovered with sequelae should be rated as an SAE since an SAE criterion is fulfilled.

Not Recovered: An AE currently ongoing.

Ongoing at final examination: An AE ongoing at the subject's last visit.

Died: An AE that caused death.

## 10.2 Recording of Adverse Events

All AEs occurring during the treatment period starting after the first vaccination at Visit 1 until termination of Visit 4 (day 182) observed by the investigator or reported by the subject (verbally or in the subject diary), will be recorded, whether or not related to the study treatment.

AEs will be requested at each visit during the treatment period up to Visit 3 (day 56) and additionally solicited by a subject's diary for 7 days after each vaccination. (see section Subject Diary)

The participants will be asked generally (e.g. "How are you?") as well as specifically (e.g. "Have you experienced any problems since the last visit?").

The investigator must record all adverse events in the eCRF. One single adverse event page must be used per adverse event, from start to resolution, stating the following information: AE description, date of onset and end date, severity, relatedness, seriousness, and action taken. Please consider definitions of section 10.1. Follow-up information should be provided, as necessary.

If possible, the investigator should record the diagnosis. If a diagnosis is not available, the investigator should record each sign and symptom as individual adverse events. However, as soon as a diagnosis becomes available, all signs and symptoms should be summarised and replaced by the underlying adverse event term (e.g. common cold instead of separate AEs for headache, rhinorrhoea, arthralgia, fever etc.)

The AE should be documented stating the highest severity (i.e. if an AE goes from mild severity to moderate severity or vice versa, the whole episode of the AE should be reported with the moderate severity). Please consider Table 5 and 6 for grading local injection site reactions and systemic reactions.

For causality reporting purposes, the categories "definitely", "probably" and "possibly" qualify an event as "suspected" adverse reaction. AEs with missing causality assessment will be regarded as possibly related unless further specified.

Any medical condition that is present at screening will be considered as medical history and not reported as an AE. However, if the subject's condition deteriorates at any time during the study, it will be recorded as an AE.

It will be left to the investigator's clinical judgment to decide whether an AE requires the subject's removal from the study. In case of discontinuation, the subject will undergo an early termination visit.

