**Safety Analysis:**

MV-ZIKA was well tolerated in this population of healthy men and women. Adverse events were predominantly mild or moderate. Only one subject experienced a severe solicited AE (fever) and five participants experienced severe unsolicited TEAEs (dysmenorrhea, arthralgia, hyperbilirubinemia, hypercholesterolemia, hyperlipidaemia and hypertriglyceridemia); all were judged unlikely or not related to IMP. No AE was judged serious.

Overall, 36 (75.0%) participants reported 200 solicited AEs and 39 (81.3%) participants reported 126 unsolicited AEs (TEAEs). The proportion of participants that experienced solicited and unsolicited AEs were higher in Group D (placebo) (100% and 87.5%, respectively) than Total ZIKA (70.0% and 80.0%, respectively). Only the proportion of participants that experienced unsolicited AEs in Group C (three high doses of MV-ZIKA [ $6 \times 10^5$  TCID50/dose]; 100%) were higher than Group D (87.5%).

Solicited local AEs occurred more frequently in participants who received MV-ZIKA than those who received placebo; more participants in Group C experienced solicited local AEs than Group A and Group B in all categories. The most frequently reported solicited local AE was injection site tenderness, followed by injection site pain. Injection site edema occurred only in Group C.

Solicited systemic AEs occurred across all treatment groups. The most frequently reported AE was headache; although the proportion of participants who experienced headache in Group D (placebo) was notably higher than any MV-ZIKA treatment group (62.5% versus 12.5–43.8%). Adverse events of myalgia, limb discomfort, rash and fever were only reported by participants who received MV-ZIKA.

The most frequently reported unsolicited AEs were nasopharyngitis and headache; the frequencies of these in participants who received MV-ZIKA were similar or less than those observed in participants who received placebo. A number of AEs were reported by participants who received MV-ZIKA but were not reported by those who received placebo. Most notably, these included general disorders and administration site conditions, and musculoskeletal and connective tissue disorders. Diarrhea was reported only by participants who received three high doses of MV-ZIKA (Group C).

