## 4.6 Benefit/Risk Assessment

### General

The measles virus vector is well known. Possible risks that are frequently associated with vaccination are the occurrence of local reactions e.g. edema, induration and erythema, transient local pain or tenderness at the injection site as well as mild to moderate headache, myalgia, flu-like symptoms or fatigue.

Currently no vaccines against Zika virus are commercially available and few vaccines are in pre-clinical or clinical testing.

The MV-ZIKA-RSP vaccine is based on the measles virus technology. [REDACTED]

[REDACTED], chemically synthesized and inserted into the Schwarz vaccine strain of measles virus (MV) to produce the candidate vaccine MV-ZIKA-RSP. Importantly, no live attenuated Zika virus is used during generation or manufacture of MV-ZIKA-RSP vaccine. Thus, induction of Zika like symptoms are not expected. However, the participants will be monitored for occurrence of adverse events and tolerability findings.

As any other vaccine, MV-ZIKA-RSP might induce allergic and anaphylactic reactions, apart from the described local reactions at the vaccination site and systemic flu-like reactions. In rare cases, the injection can lead to a vasovagal reaction immediately after injection of the vaccine. The needle pricks for blood sampling may also cause local reactions such as edema. The participants cannot expect direct benefit from study participation, except for potential boosting of measles immunity and mounting immunity to Zika virus.

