## 11.7 Subject Diary

The participants will be instructed to complete a diary for 7 days after each vaccination to document local and systemic tolerability as well as body temperature.

Solicited local and solicited systemic AEs will be assessed by the participants themselves by checking for presence of the listed symptoms and measuring the size of the affected area where appropriate (a template will be provided for local reaction grading, as shown in Appendix 1). The diary will also provide space for recording unsolicited AEs and concomitant medication.

Recording should be done approximately at the same time each day, starting on the day of vaccination. The first entry should be made 6 hours  $\pm 1$ h after vaccination at Visit 1 and Visit 2.

The participants' diaries will be collected and verified for completeness by the investigator at Visit 2 and Visit 3. Any AE recorded in the subject diaries will be entered in the eCRF by the investigator or authorised delegates. The investigator will re-evaluate the severity of the reported local and systemic AEs according to the below Tables 5 and 6.

Diary solicited systemic AEs include nausea, vomiting, headache, and fatigue, also to be documented in the eCRF.

In addition, body temperature will be recorded daily for 7 days and fever will be graded by the investigator according to the FDA Guidance for Industry. For details see below Table 6. Table 5. Grading of local reactions

| Local reaction to injectable product | Mild (grade 1) | Moderate (grade 2) | Severe (grade 3) | Potentially life threatening (grade 4) |
|--------------------------------------|----------------|--------------------|------------------|--|
|--------------------------------------|----------------|--------------------|------------------|--|

|   |   |  |  |  |
|---|---|--|--|--|
| Pain                             | Does not interfere with activity            | Interfere with activity or repeated use of non-narcotic pain reliever  | Prevents daily activity or repeated use of non-narcotic pain reliever                    | Emergency room (ER) visit or hospitalisation |
| Tenderness                       | Mild pain to touch                          | Pain with movement   | Significant pain at rest   | ER visit or hospitalisation                  |
| Erythema/ Redness    | ≤ 5 cm                                      | 5.1–10 cm  | > 10 cm  | Necrosis or exfoliate dermatitis             |

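### Protocol 10.2 replaces symptoms by a diagnosis without exempting solicited diary events, conflicts with 11.7 and 12.3, and so can understate solicited systemic rates and fever grades

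*Combined protocol and SAP*

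**What the plan says.** Protocol 10.2 (Recording of Adverse Events) covers events reported verbally or in the diary. Its default is: "If a diagnosis is not available, the investigator should record each sign and symptom as individual adverse events". It then reverses this once there is a diagnosis: "all signs and symptoms should be summarised and replaced by the underlying adverse event term (e.g. common cold instead of separate AEs for headache". The example in full is "common cold instead of separate AEs for headache, rhinorrhoea, arthralgia, fever etc". The section makes no distinction between solicited and unsolicited symptoms.

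Protocol 11.7 (Subject Diary) says: "Any AE recorded in the subject diaries will be entered in the eCRF by the investigator or authorised delegates". It adds: "Diary solicited systemic AEs include nausea, vomiting, headache, and fatigue, also to be documented in the eCRF". Temperature is taken daily for 7 days, and the investigator grades fever from it under Table 6.

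Protocol 12.3 summarises solicited local and systemic AEs from the diaries for the 7-day period, by grade and treatment group.

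SAP 7.1 plans solicited systemic AEs by symptom (Tables 1.4.1.9 and 2.4.1.9) and by symptom and maximum severity (Tables 1.4.1.12 and 2.4.1.12). The solicited listings in SAP 7.2 (1.4.19 onwards, 2.4.19 onwards) consist of AE-record fields such as term, severity, seriousness and causality.

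**The concern.** Solicited reactions are normally counted whatever their presumed cause, so that the comparison with placebo shows what the vaccine does. A rule that replaces the symptom by a diagnosis puts a judgement of cause ahead of that comparison.

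The judgement is not an easy one here. The benefit/risk section (4.6) warns of allergic reactions "apart from the described local reactions at the vaccination site and systemic flu-like reactions", and it names headache, myalgia and fatigue among the common risks of vaccination. In the first days after an injection, reactogenicity and a cold can look alike. Diaries are collected and re-evaluated at Visits 2 and 3, so a diagnosis may be made in retrospect.

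The results at stake are the solicited AE rates compared between the four groups (a secondary endpoint in 6.2.2), the by-symptom and by-grade tables, and the tolerability part of the dose objective in 5.2.

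**Working it through.** The documents give no figure to reproduce on this point. The check is textual, with simple arithmetic for scale.

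**1. Does the 10.2 rule reach solicited events?** Yes, as written. It covers diary-reported AEs and has no exemption. Of the four symptoms in its example, headache is a listed solicited systemic AE and fever is measured in the diary. Rhinorrhoea and arthralgia are not on the solicited list in 11.7.

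**2. Can 10.2 and 11.7 both be followed?** Only by reading them in sequence: enter the diary symptom first, then replace it when a diagnosis appears. The symptom then no longer stands as a solicited AE, which defeats the 11.7 requirement to document it and the 12.3 requirement to summarise it. If 11.7 prevails, the symptom stays. The documents do not say which applies, so the site decides case by case.

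**3. Would the SAP recover a replaced symptom?** It has no provision to do so.
- The solicited listings hold AE-record fields, and SAP 7.2 plans no diary listing.
- Temperature is tabulated only by visit (Table 1.4.1.43). Daily diary temperatures have no table or listing, so a diary fever shows only as an AE record.
- A single cold record cannot fill the headache, fatigue or fever rows of a by-symptom table.
- SAP 2.8 deals with a missing solicited/unsolicited assignment. It does not deal with a diagnosis that replaces solicited symptoms.

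**4. Can the grade change?** Yes. Table 6 grades fever by temperature, with 39.0–40.0 °C as grade 3. It grades illness by function, with some interference and no medical intervention as grade 2. A hypothetical fever of 39.2 °C is grade 3 as fever but fits grade 2 if merged into such an illness. The highest-severity rule in 10.2 is about how one AE evolves. It does not say that the grades of component symptoms carry over.

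**5. Size per participant.** SAP 6.2.2 uses group totals as denominators: 14, 14, 12 and 8. Recoding one participant lowers a rate by at most 1/n:

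| Group | n | 1/n |
|---|---|---|
| A, B | 14 | 7.1 points |
| C | 12 | 8.3 points |
| D | 8 | 12.5 points |

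This is a maximum. The overall solicited systemic rate falls only if the participant has no other solicited systemic AE in either diary window. A single symptom row falls only if the same symptom is not retained from the other window.

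**6. Equal loss in all arms.** Equal loss still shrinks a difference. With assumed true symptom rates of 50% and 25% and a share s retained in both arms, the difference is (0.50 − 0.25) × s. That is 25 points at s = 1, 22.5 at s = 0.9 and 17.5 at s = 0.7. Both the rates and the shares are assumptions.

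**7. Primary endpoint.** A recoded participant had at least one AE before recoding and has at least one after. With x participants having any AE, x/n is unchanged, provided the replacing record falls in the day-56 window.

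**The case against.** The strongest reply is that 11.7 is the specific section on diaries and 12.3 the specific section on their analysis, so they should govern over a general recording rule. On that reading nothing is lost. SAP 2.14 also declares no change from the protocol analysis, and completed diaries are kept as source records (15.1). This is a fair reading and it rules out treating the loss as certain. It does not settle the matter, because 10.2 expressly includes diary events and uses headache and fever as its example.

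The trigger is also narrow. A diagnosis must be made, and the example is an intercurrent infection. Without a diagnosis each symptom stays separate, and local reactions are hardly affected. All of this stands and limits the size of the problem.

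A reader might infer that the loss falls mainly on the vaccine arms. The documents do not support that. The assessor is blinded (8.3). In the predecessor trial, "The most frequently reported unsolicited AEs were nasopharyngitis and headache", but the same sentence says that their frequency under MV-ZIKA was similar to or below that under placebo. Solicited AEs there occurred in 100% of placebo participants against 70.0% of vaccinees, and headache in 62.5% against 12.5–43.8%. Fever and myalgia were seen only after MV-ZIKA, so the picture is mixed.

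A reader might also infer that replacement weakens the individual stopping rule in 8.9.1. That rule concerns grade 4 solicited systemic reactions and already requires that no other cause explains them. A symptom put down to a cold is outside it whichever term is recorded.

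**Conclusion.** The point holds as an unresolved contradiction with a possible loss of data. Section 10.2 conflicts with 11.7 and 12.3, and the SAP has no rule that would detect or correct the consequence. If a diagnosis is made within 7 days of an injection and 10.2 is applied, solicited systemic rates, by-symptom rates and fever grades can be understated in any arm. The maximum per recoded participant is 7.1 points in A or B, 8.3 in C and 12.5 in D. The number of such participants is unknown, so no total can be given.

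Two stronger readings are not supported. One is that the primary result is biased: the participant-level any-AE rate to day 56 stays the same. The other is that these events become unsolicited illnesses. That is plausible, but neither document says how the replacing term is classified, and this silence is part of the defect.

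The change is worth making because solicited rates are a secondary endpoint, groups are small, and the remedy costs almost nothing.

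**What to change.** **Protocol 10.2.** Reconcile it with 11.7 and 12.3 by adding: *The replacement rule does not apply to solicited symptoms or fever with onset in the 7-day diary window after an injection. These remain separate solicited AEs with their own Table 5 or Table 6 grade. Any diagnosis is recorded in addition.* The replacement rule can stay for unsolicited symptoms.

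**SAP.** State that the solicited tables count these separate records, say how the additional diagnosis is classified, and state that each participant is counted once in any-AE summaries.

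**Cost.** One sentence in the protocol and a short statement in the SAP, plus matching eCRF instructions. Event counts rise slightly because symptom and diagnosis are both recorded. The participant-level any-AE count does not rise. Where symptoms have already been replaced, the retained diaries allow them to be restored.
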